9.5.2 Physician completed assessments

In accordance with the requirements for application for renewal of subsidy by Special Authority, a measure of disease activity will be administered within 3–6 months of initiation.

9.6 Study Size

It is anticipated that the three groups will respond differently to adalimumab treatment over the study period and there is reason to believe that these groups will be different at baseline. Therefore, the sample size will be powered for rheumatoid arthritis and Crohn's disease. Approximately 80 subjects will be enrolled into each of these 2 parallel study groups allowing for detection of within participant effect sizes of approximately 0.40 as statistically significant (2-tailed $\alpha=0.05$) with 90% power. A minimum of 30 subjects with psoriasis will also be enrolled. A minimum number of 190 patients will be enrolled into the study. The maximum number of rheumatoid arthritis and Crohn's disease patients will be N=100 in each arm, respectively.

Psoriasis patients make up a much smaller proportion of the population who currently receive adalimumab therapy in New Zealand. Therefore, a smaller number of patients (N=30) are sought to be enrolled in this study to ensure the trial population is representative of the general patient population. The maximum number of psoriasis patients will be N=50.

9.7 Data Management

9.7.1 Data Collection

The Investigator must maintain required records on all study subjects. Data for this study will be recorded in the subject's medical records, study-specific worksheets, CRFs and on electronic patient questionnaires provided by Sponsor. All data on the CRFs should be recorded with appropriate source documentation. Upon study completion or at any other time specified by the sponsor, a monitor will verify the source documentation records and review the data, under the responsibility and authority of the Investigator. The monitor will collect the appropriate CRF pages and a complete set of copies will remain at the investigational site with any related data clarification forms (DCF).

9.7.2 Data Correction

Corrections of data entered on original source documents and CRFs must be made in the following manner:

- The incorrect entry must be crossed-out with a single line. The correct data should then be entered next to the entry crossed-out. Each correction, change or addition of new data must be initialed and date by the individual making the correction / alteration.
- Completed source document/CRFs should be ready for review by the Sponsor monitor approximately within a week of each study visit for a given subject, unless the forms are incomplete because of laboratory data or adverse event follow-up that is not yet available.
- The Sponsor will review the source documents/CRFs, evaluate them for completeness and accuracy, and ensure all corrections are made to either the CRF or other designated clarification form.
- Any changes made to the CRF after collection by the Sponsor monitor will be discussed and approved by the Investigator (or designee) and corrected on a DCF.

9.7.3 Source Documentation

Investigators must keep accurate separate records (other than the CRFs) of all subjects' visits, being sure to include all pertinent study related information. A statement should be made indicating that the subjects have been enrolled in Protocol and have provided written Informed Consent. Any and all side effects and adverse events must be thoroughly documented. Telephone conversations with the subjects concerning the study must also be recorded.

The Investigator is responsible for maintaining a Subject Identification Log, which will include all subjects who provided informed consent (i.e. to include randomized subjects and screening failures). This confidential subject identification code provides the link between named subject source records in the subject file and anonymous CRF and questionnaire data provided to the sponsor

The Investigator must retain all study related documentation until at least two years after at least two years have elapsed since the formal discontinuation of the clinical study. Study documents should not be destroyed without prior written agreement between the

Investigator and the sponsor. The sponsor must be notified if the Investigator wishes to assign the study records to another party, or move them to another location.

9.8 Data Analysis

9.8.1 Definitions

9.8.1.1 Participant Population

All participants who are recruited into the study and start study medication will be used for analysis. A full analysis set will be used for the analysis of the efficacy outcomes with all available data used for the analyses of each outcome at the relevant time points. Efficacy measures are not assessed after a participant discontinues adalimumab. The exception to this will be the analysis of proportion of patients at 6 months who remain on adalimumab, having satisfied the requirements for application for renewal of subsidy by Special Authority. Any participants for whom this assessment is not available will be assumed to have not met these requirements. The primary population for the evaluation of study safety objectives will be the safety population, defined as all participants enrolled into the trial who started study medication. Safety outcomes will only be considered while the patient is on adalimumab. A standard consort diagram describing participant flow (including loss to follow-up and discontinuations for any reason) through the study will be generated.

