9.5 Data Sources

Designated investigator staff will collect data required by the protocol on paper Case Report Forms (CRFs). Collection of data includes but not limited to subject demographics, adverse events, serious adverse events and concomitant medications. Designated investigator staff should not enter any data until they have completed appropriate training. The sites are requested to send a copy of the CRF (scanned copy is acceptable) through to the Data Manager to enter into the database within 10 working days. Where there are discrepancies with the data, data clarification forms should be raised for the designated investigator staff to clarify and return to the Sponsor.

9.5.1 Questionnaires:

Subject self-assessment questionnaires will be utilized in this study to determine patients' improvement over time. Patients will require Internet access as the questionnaires are administered electronically through an online portal. For patients unable to utilize the online questionnaires paper-and-pencil versions of questionnaires will be provided and can be self-administered in person in a quiet and private area of the clinic. In addition, for subjects completing paper and pencil versions, the questionnaires can be administered over the telephone if the questionnaire time-point does not coincide with a clinic visit. Data collected via paper and pencil versions of the questionnaires will be transcribed by site staff into the online portal on behalf of the patient. Data will be retrieved directly by the Data Manager for analysis. Based on a pilot evaluation of the study questionnaires in a small number of patients, they are expected to take approximately 10 minutes per visit, per subject, to administer. Patients should ensure that their subject number and the date the questionnaire was completed is entered onto the questionnaire.

Each patient will complete six (6) common questionnaires at Baseline, Month 2, Month 4 and Month 6:

- WHODAS 2.0
 - Covers six different domains: cognition, mobility, self-care, getting along, life activities and participation.
 - Does not have a set cut point to define disability
 - 12 items

- WPAI:GH V2.0
 - This questionnaire looks at the effect of health problems on ability to work and perform regular activities.
 - Time missed from work, impairment of work
 - 6 items
- K10

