9.9 Missing Data

Efficacy measures are not assessed after a participant discontinues adalimumab. The exception to this will be the analysis of proportion of patients at 6 months who remain on adalimumab, having satisfied the requirements for application for renewal of subsidy by special authority. Any participants for whom this assessment is not available will be assumed to have not met these requirements. There will be no other imputation for missing data.

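### The month-6 WHODAS estimate makes no use of month-2 and month-4 scores from patients still on adalimumab who miss the month-6 questionnaire

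*Combined protocol and SAP*

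**What the plan says.** WHODAS 2.0 and the other questionnaires are scheduled at baseline and months 2, 4 and 6 (Section 9.1 and Table 2). The primary outcome is the month-6 change alone (Section 9.8.4). The month-2 and month-4 changes are separate secondary endpoints (Section 9.8.5).

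On data use, Section 9.8.1.1 specifies a full analysis set with "all available data used for the analyses of each outcome at the relevant time points". Section 9.9 imputes only the Special Authority proportion and adds: "There will be no other imputation for missing data". Efficacy is not assessed after a patient stops adalimumab.

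On method, Section 9.8.4 gives a general linear model with participant, indication and baseline WHODAS as terms. It has no visit term and no covariance structure. The abstract (Section 4.0) instead gives a paired t-test in patients continuing on adalimumab.

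On collection, Section 9.5.1 states: "Patients will require Internet access as the questionnaires are administered electronically through an online portal". It then allows paper forms in clinic and telephone completion. Section 9.2.2 lists study visits at months 2, 4 and 6 with a seven-day window.

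**The concern.** The estimate rests on patients with a month-6 score. The best available predictor of a missing month-6 score is the same patient's month-4 score, which was collected and is not used. Two things are at stake.

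- **Precision.** Information already in the database is discarded.
- **Bias.** This is an uncontrolled before–after study whose headline is a mean change. If patients doing poorly at month 4 are less likely to answer at month 6, the respondents' mean is too favourable, and no comparator absorbs the error.

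Section 9.8.1.1 also promises that everyone who starts medication enters the analysis. An estimate from month-6 respondents alone does not deliver that.

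The point is confined to missed questionnaires in patients still on adalimumab. Patients who stop raise a different question, because no efficacy data are collected after stopping.

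**Working it through.** **1. Does any reading of Section 9.8.4 use the earlier scores?**

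- *One change score per patient.* A fixed participant term plus indication and baseline leaves 0 residual degrees of freedom, so the model cannot be fitted as literally written.
- *Baseline and month-6 rows.* Months 2 and 4 are not used.
- *All visits stacked.* With no visit term, the model estimates an average over visits, not the month-6 change.
- *The abstract's paired t-test.* It needs both the baseline and the month-6 score.

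No reading that gives the stated endpoint brings in month 2 or month 4.

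**2. The planned size.** Section 9.6 states: "Approximately 80 subjects will be enrolled into each of these 2 parallel study groups", to detect "within participant effect sizes of approximately 0.40" as "statistically significant (2-tailed $\alpha=0.05$) with 90% power". For a paired test, the normal approximation gives n = ((1.960 + 1.282)/0.40)² = 65.7, so 66; the t distribution gives 68. At n = 80 the power is 94.2%. The stated inputs alone therefore do not reproduce 80 at 90%, but 68/(1 − 0.15) = 80 does. The figure is conservative, and this point does not depend on it. Section 9.6 also states: "A minimum of 30 subjects with psoriasis will also be enrolled", and "A minimum number of 190 patients will be enrolled into the study".

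**3. Power using month-6 respondents only** (paired t, effect 0.40; missing rates assumed):

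| Missing | n of 80 | Power | n of 190 |
|---|---|---|---|
| 0% | 80 | 94.2% | 190 |
| 10% | 72 | 91.7% | 171 |
| 15% | 68 | 90.2% | 162 |
| 20% | 64 | 88.3% | 152 |
| 30% | 56 | 83.7% | 133 |

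Pooled power is at least 99.6% throughout. Within rheumatoid arthritis or Crohn's disease it falls below 90% once more than about 15% are missing.

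**4. Precision.** Let m be the proportion missing month 6 at random, and ρ the correlation of month-4 and month-6 change. Every non-responder is taken to have a month-4 score. Variance of the month-6 mean relative to full data:

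- available cases: 1/(1 − m)
- repeated measures: (1 − ρ²)/(1 − m) + ρ²

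At m = 0.15 and ρ = 0.7 these are 1/0.85 = 1.176 and 0.51/0.85 + 0.49 = 1.090. The reduction is ρ²m = 0.49 × 0.15 = 7.4%, or 190/1.090 − 190/1.176 = 12.8 patients. The range runs from 0.25 × 0.10 = 2.5% (about 4 patients) to 0.64 × 0.25 = 16% (about 27). The patient counts take all 190 as still on drug, so they are upper figures.

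**5. Bias.** Simulation with a true improvement of 0.40 SD, 15% missing and ρ = 0.7; improvement is shown as positive:

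| Non-response depends on | Log-odds per SD | Available cases | Using month 4 |
|---|---|---|---|
| Month-4 change | 0.5 | 0.45 | 0.40 |
| Month-4 change | 1.0 | 0.49 | 0.40 |
| Month-6 change itself | 0.5 | 0.47 | 0.44 |
| Month-6 change itself | 1.0 | 0.53 | 0.47 |

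Under the first mechanism, over 10–25% missing and ρ of 0.5–0.8, the available-case mean runs from 0.42 to 0.57. At 5% missing and ρ = 0.7 the bias is only about 0.02–0.03.

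**6. Which patients to fit it in.** Assume 25% stop adalimumab, more often after a poor month-4 change (log-odds 1 to 2 per SD), with ρ = 0.7 and 15% random non-response among the rest. The true month-6 mean in patients still on drug is then 0.55–0.62 SD. A repeated-measures model on all starters returns 0.40, because it predicts stoppers' month-6 scores as if they had continued. Restricted to patients still on drug, it returns 0.55–0.62. When non-response in that group is made to depend on month-4 change, the restricted model also removes the resulting bias of 0.04–0.08 SD.

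**The case against.** The strongest reply is that separate modelling of each visit is an inference. The participant term makes sense only with several rows per patient, so a repeated-measures analysis may have been intended, and a likelihood-based model is not imputation and is not excluded by Section 9.9. It stands that the documents do not state separate per-visit models. It does not follow that the earlier scores are used: without a visit term or covariance structure, no reading gives a month-6 estimate that draws on them.

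A reader might also infer that month-6 non-response is likely, since Table 1 has only one follow-up clinic column, at 3–6 months. The documents do not support that. Section 9.2.2 lists a month-6 visit, Table 2 schedules the month-6 questionnaires, Section 9.5.1 offers paper and telephone completion, and Section 9.11 has the sponsor check questionnaires for completeness. The rate is unknown and could be low.

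A reader might further infer that a repeated-measures model recovers the truth. It does so in the simulation only when non-response depends on observed scores.

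The objection that a model on all starters would quietly change the estimand stands in full. Continuation depends on response between 3 and 6 months, and the abstract defines the primary population as patients continuing on adalimumab.

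The month-2, month-4 and month-6 means may come from different sets of patients, but this is minor: no between-visit comparison is planned, and a participant-flow diagram is.

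**Conclusion.** The concern holds in limited form. A patient still on adalimumab without a month-6 WHODAS contributes nothing to the primary estimate, and collected scores that could inform it go unused. No sensitivity analysis for missed questionnaires is planned.

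The case rests on bias, not power. At an assumed 15% missing, ρ = 0.7 and log-odds of 0.5–1.0 per SD of poor month-4 change, the improvement is overstated by about 0.05–0.09 SD on 0.40. The precision loss is about 7% (range 2.5–16%), and pooled power is hardly affected. The non-response rate, the correlation and the mechanism are all assumptions, because the documents give none of them. The change is worth making before analysis, but it does not show the primary result to be unreliable.

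**What to change.** 1. In Section 9.8.4, specify a mixed model for repeated measures on WHODAS change at months 2, 4 and 6. Include visit, indication, baseline score, indication-by-visit and baseline-by-visit, with an unstructured covariance. The month-6 mean change with its 95% confidence interval is the primary estimate.
2. Fit it in patients still on adalimumab at month 6, whether or not they returned the month-6 form, and state that this is the estimand. Scores from patients who stopped are then not used to predict a month-6 value as if treatment had continued.
3. Keep the available-case month-6 analysis as a sensitivity analysis.
4. Reconcile Section 9.8.4 with the abstract on both method and population. This is needed in any case, since the two differ and the written model cannot be fitted to one change score per patient.

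The cost is analysis-plan wording and modest programming; no new data are needed. The downside is the assumption that non-response among on-drug patients is explained by observed scores. That is weaker than what the respondents-only analysis assumes, but if non-response depends on month-6 status itself, the bias is reduced, not removed.

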Data Sources: Case Report Forms (CRFs). Collection of data includes but not limited to subject demographics, adverse events, serious adverse events and concomitant medications. The following questionnaires will be utilized to collect data directly from participating subjects:

- WHODAS 2.0
- WPAI:GH V2.0
- K10
- Flourishing Scale
- Subject Vitality Scale
- Disease-specific PROs that are commonly used in clinical practice (HAQ-DI, SIBDQ, DLQI)

Study Size: It is anticipated that the three groups will respond differently to adalimumab treatment over the study period and there is reason to believe that these groups will be different at baseline. Therefore, the sample size will be powered for rheumatoid arthritis and Crohn's disease. Approximately 80 subjects will be enrolled into each of these 2 parallel study groups allowing for detection of within participant effect sizes of approximately 0.40 as statistically significant (2-tailed $\alpha=0.05$) with 90% power. A minimum of 30 subjects with psoriasis will also be enrolled. A minimum number of 190 patients will be enrolled into the study.

Data Analysis: Primary Endpoint Analysis

Change in total WHODAS 2.0 score at 6 months after the initiation of adalimumab, in those patients continuing on adalimumab (responder population), across all indications. This change will be summarised as the mean and 95% confidence interval and will be tested with a paired t-test.

Secondary Endpoint Analyses

- Change in disease-specific indices (HAQ-DI, SIBDQ, DLQI), WPAI:GH, K10, Flourishing Scale, Subject Vitality Scale at 2, 4 and 6 months after the initiation of adalimumab, in those patients continuing on adalimumab (responder population). These changes will be summarised as the means and 95% confidence intervals and will be tested with paired t-tests.
- Change in total WHODAS 2.0 score at 6 months after the initiation of adalimumab, in those patients continuing on adalimumab (responder population), compared with those patients not continuing on adalimumab (non-responders). The mean changes in these two groups will be compared using an independent t-test.

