As this is a non-interventional, observational study, no restrictions on dose modification or concomitant medications will be imposed at any time throughout the course of the study. Administration of adalimumab and follow up visits will be carried out according to investigators’ normal practice.

Primary Endpoint

Change in total WHODAS 2.0 score at 6 months after the initiation of adalimumab, across all indications.

Secondary Endpoints

- Change in total WHODAS score 2 and 4 months after the initiation of adalimumab across all indications
- Change in total WHODAS score 6 months after the initiation of adalimumab in each indication
- Changes in WPAI:GH V2.0 Scores, K10 scale, Flourishing Scale, Subject Vitality Scale at 6 months after the initiation of adalimumab, across all indications
- Change in disease-specific scores (HAQ-DI, SIBDQ, DLQI) at 6 months after the initiation of adalimumab, in each indication
- Proportion of patients at 6 months who remain on adalimumab, having satisfied the requirements for application for renewal of subsidy by “Special Authority”:
 - Rheumatoid arthritis: $\geq 50\%$ decrease in active joint count from baseline AND a clinically significant response to treatment in the opinion of the physician
 - Crohn’s disease: Crohn's Disease Activity Index (CDAI) score reduction by 100 points or CDAI score ≤ 150

- Psoriasis: Psoriasis Area and Severity Index (PASI) score reduction of $\geq 75\%$; or in the case of a patient had severe chronic plaque psoriasis of the face, or palm of a hand or sole of a foot at the start of treatment, the patient has a reduction in the PASI symptom subscores for all 3 of erythema, thickness and scaling, to slight or better, OR $\geq 75\%$ reduction in affected skin area.

No restriction on current standard of care is imposed. Physicians should treat their patients as they would in their routine clinical practice. Prior medical history, the use of any concomitant medication and any and all adverse events will be captured and recorded in the CRF.

As all procedures will be conducted in accordance with routine medical practice, participation in the study does not convey any additional risks for the subject. However, the subject will be provided with information on the benefits and risks of their medical treatment by the physician, in accordance with their routine medical practice.

Prior to collecting any study related information, written informed consent must be obtained.

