9.8.2 Statistical Analyses

The primary analysis of study efficacy measures will be performed using the full analysis set.

Tables showing standard descriptive statistics (including means, standard deviations, standard errors, medians, ranges and frequencies and percentages), graphs, and participant data listings will be used to summarize the baseline demographic and clinical characteristics, and the efficacy and safety data at relevant time-points. Tabular and graphical summaries will represent data separately for each indication group.

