9.8.4 Primary Efficacy Analyses

The primary efficacy outcome is the change in the total WHODAS 2.0 score at 6 months after the initiation of adalimumab, across all indication groups. This change will be summarised as the mean and 95% confidence interval and will be tested with a general linear model which includes participant, indication and baseline WHODAS 2.0 score as terms in the analysis.

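### The plan names two primary populations and two primary tests, and if nothing is measured after adalimumab stops, the month-6 full-analysis-set mean comes mainly from responders

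*Combined protocol and SAP*

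**What the plan says.** **Primary analysis, Abstract (4.0).** The month-6 change is analysed "in those patients continuing on adalimumab (responder population), across all indications" and "will be tested with a paired t-test". A secondary analysis takes the month-6 change in continuers "compared with those patients not continuing on adalimumab (non-responders"), using an independent t-test.

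**Primary analysis, body.** Section 9.1 gives the primary endpoint as "Change in total WHODAS 2.0 score at 6 months after the initiation of adalimumab, across all indications", with no restriction to continuers. Section 9.8.1.1 says "All participants who are recruited into the study and start study medication will be used for analysis". Section 9.8.2 says "The primary analysis of study efficacy measures will be performed using the full analysis set". Section 9.8.4 has the change "tested with a general linear model which includes participant, indication and baseline WHODAS 2.0 score as terms in the analysis". The list of secondary analyses in 9.8.5 does not contain the comparison with non-continuers.

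**Collection after drug stop.** Section 9.8.1.1 states "Efficacy measures are not assessed after a participant discontinues adalimumab", and 9.9 repeats it. Section 9.8.1.2 ends observation when study medication stops. Section 9.9 allows no imputation for WHODAS. On the other side, Table 2 (9.1.1) schedules the questionnaires at month 6 without an on-drug condition, and 9.5.1 has each patient complete them at baseline and months 2, 4 and 6.

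**Continuation.** The Abstract and 9.1 make continuation depend on meeting response criteria between 3 and 6 months. Table 1 lets that assessment fall anywhere in this interval.

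**The concern.** Two matters need settling. The first is textual: current sections give different primary populations, different primary tests and conflicting rules on whether WHODAS is collected after drug stop. None of this comes from the amendment list in Annex 2.

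The second is what the body's label would mean in practice. A full analysis set of all starters suggests a month-6 mean for everyone who began treatment. If scores stop with the drug, and the drug stops mainly for lack of response, the participants with a month-6 score are mostly those who responded. The objective (8.0) and hypothesis (8.1) are not limited to continuers. A reader of the final report could therefore take a mean among patients still on drug as the change to expect on starting adalimumab.

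**Working it through.** **1. Who has a month-6 score under 9.8.1.1, 9.8.1.2 and 9.9?** Participants still on adalimumab at month 6. These are responders plus any non-responders not yet stopped, for example those assessed late in the 3-to-6-month interval. Hence mainly responders, not only responders.

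**2. How far apart are the two named primaries?** Under the same rules both populations reduce to nearly the same participants. The tests can also nearly agree. A linear model on the change score, with baseline and indication centred at their sample means, returns the plain mean change as its intercept, so only the standard error differs from the paired t-test. Another weighting, such as equal weight per indication, could move the estimate, and 9.8.4 does not specify one.

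**3. The participant term in 9.8.4.** With one change score per participant, this term uses up all the data. It needs at least two records each. Baseline and month-6 records with a time term would reproduce the paired t-test. Adding months 2 and 4 would give a repeated-measures analysis. Section 9.8.4 names neither a time term nor the visits used. The figures in steps 4 and 5 assume month-6 data only.

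**4. Continuers against all starters.** The documents give no figure to reproduce here. The only scale available is the planning effect of 0.40 (9.6).

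Inputs, all assumed: p = proportion continuing; f = mean change in stoppers divided by mean change in continuers; no stoppers measured at month 6.

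All-starter mean = p × continuer mean + (1 − p) × stopper mean, so continuer mean / all-starter mean = 1 / [p + f(1 − p)].

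| p | f = 0 (stoppers unchanged) | f = 0.5 | f = 1 (stoppers improve equally) |
|---|---|---|---|
| 0.90 | 1.11 | 1.05 | 1.00 |
| 0.80 | 1.25 | 1.11 | 1.00 |
| 0.70 | 1.43 | 1.18 | 1.00 |
| 0.60 | 1.67 | 1.25 | 1.00 |

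If the all-starter change were 0.40 and stoppers were unchanged, continuers would show 0.40/p: 0.44 at p = 0.90 and 0.67 at p = 0.60.

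If a share q of stoppers does have month-6 data and f = 0, the ratio is 1 / [p + q(1 − p)]. At p = 0.70 it falls from 1.43 to 1/0.775 = 1.29 for q = 0.25, and to 1/0.85 = 1.18 for q = 0.50.

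**5. The same question through a correlation.** Suppose disease response and WHODAS improvement are bivariate normal with correlation ρ, and the top fraction p continues. The excess in the continuer mean is ρφ(z)/p SD of change, with z = Φ⁻¹(1 − p).

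- ρ = 0: 0 at any p.
- p = 0.70, ρ = 0.3: z = −0.524, φ(z) = 0.348, excess 0.3 × 0.348/0.70 = 0.15 SD.
- p = 0.60, ρ = 0.7: excess 0.45 SD. Stoppers then lie 0.68 SD below the all-starter mean, so with a mean of 0.40 they would worsen by 0.28 SD.

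**6. If months 2 and 4 enter the model.** Illustration: p = 0.70, ρ = 0.3 at month 6 and 0.2 to 0.3 at months 2 and 4, all-starter mean 0.40 at each visit, correlation between visits 0.3 to 0.7. Continuers alone give 0.55. A likelihood-based repeated-measures model without off-drug scores gives 0.43 to 0.52. The model reduces the excess but does not remove it.

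**The case against.** The strongest reply is that change on drug is a legitimate target and that the plan discloses it. The Abstract names the continuer population, 9.8.1.1, 9.8.1.2 and 9.9 state the cut-off, and the flow diagram and the proportion remaining on drug will show the attrition. The hypothesis can be read as referring to patients under treatment. This stands as a defence of the target. It does not reconcile the Abstract with 9.8, and disclosed attrition does not change what the month-6 mean describes.

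A reader might infer from the two definitions that two analysts would report materially different primary results. The documents do not support that. Under the no-assessment rule the two populations nearly coincide, and the tests can agree closely (steps 1 to 3). The gap that matters is between continuers and all starters, and neither named analysis would estimate the latter.

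A reader might also infer that every non-responder is lost at month 6. Table 1 does not support that, because the response assessment may come late. Nor is non-collection after drug stop beyond doubt: Table 2, 9.5.1 and the planned comparison with non-continuers point the other way, and stopping adalimumab is not itself listed as a reason for mandatory study withdrawal in 9.1 or 9.2.3. The explicit statements in 9.8.1.1, 9.8.1.2 and 9.9 probably govern, but the plan should say so.

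**Conclusion.** The inconsistency is established from the current text: two primary populations, two primary tests, conflicting rules on collection after drug stop, and a comparison with non-continuers that appears only in the Abstract. If 9.8.1.1, 9.8.1.2 and 9.9 govern, the month-6 full-analysis-set mean comes mainly from responders, it describes change in patients still on adalimumab, and the comparison with non-continuers has little or no data.

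Whether and by how much this overstates change among all starters cannot be determined from the documents. The direction requires WHODAS change to be positively related to disease response. The range of 1.00 to 1.67 assumes 60 to 90% continuing, no stoppers measured, and stoppers who on average do no worse than stay unchanged and no better than continuers. It should not be read as an estimate of bias in this study. With no untreated control, neither target isolates a drug effect.

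**What to change.** **Required.**

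1. State one primary population and one primary test.
2. Make the Abstract, 9.1.1, 9.5.1, 9.8.1.1, 9.8.1.2, 9.8.2, 9.8.4, 9.8.5 and 9.9 agree on these and on whether WHODAS is collected after drug stop.
3. Say in 9.8.4 which visits enter the model, in particular whether months 2 and 4 do, so that the participant term has a meaning.
4. If scores after drug stop are not collected, restrict the objective and conclusion to patients continuing adalimumab, delete the comparison with non-continuers, and state the selection under 9.12, which shows no text in the copy supplied.

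On the non-collection route this costs wording only.

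**Optional.** Keep the scheduled WHODAS after drug stop for participants who still consent. Estimate month-6 change in all starters with a likelihood-based repeated-measures model on baseline and months 2, 4 and 6, and report the on-drug result as supplementary.

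This is a design choice with real costs. It needs a mid-study amendment reversing 9.8.1.2 and possibly a consent update. No scores can be recovered from participants who have already stopped and passed their visits. Some will not reply, and reply may depend on score. Off-drug scores will reflect later treatment. The 30-day call in 9.2.3 is for adverse events and is not timed to the questionnaires, and 9.5.1 describes telephone administration only for paper users, so the collection route would also have to be specified. Nothing here bears on who should continue adalimumab.
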